## 17.6. VITAL SIGNS

The following Vital Signs measurements will be reported:

- Systolic Blood Pressure (mmHg)
- Diastolic Blood Pressure (mmHg)
- Pulse Rate (bpm)
- Respiratory Rate (resp/min)
- Temperature (°C)
- Weight (kg)
- BMI (kg/m^2)

Actual results and change from baseline by visit will be summarized. All vital signs data will be listed.

## 17.7. PHYSICAL EXAMINATION

The physical examination data will be listed.

---

HUTCHMED Ltd.

CONFIDENTIAL

HMPL-523

---

### **17.8. SPLEEN AND LIVER ASSESSMENT**

The Spleen and Liver Assessment data will be listed.

### **17.9. ECOG PERFORMANCE STATUS**

The incidence of ECOG performance status will be presented by visit. In addition, ECOG performance status will be presented using shift table to compare baseline to the worst post-baseline value. Values from post-baseline unscheduled visit will be considered when deriving worst post-baseline value.

All ECOG data will be listed.

### **17.10. ECHOCARDIOGRAM/MUGA**

The Echocardiogram/MUGA data will be summarized by visit (descriptive statistics) and listed.

HMPL-523

---

## 18. PHARMACOKINETIC ANALYSIS

PK parameters will be analyzed with the PKAS. A noncompartmental model analysis will be performed for plasma concentration data by a central laboratory using Phoenix WinNonlin. Individual and mean plasma concentration of HMPL-523 and its metabolites versus time data will be tabulated and presented. The individual and mean PK parameters determined following analysis of the concentration of HMPL-523 and its metabolites versus time data will include, but not be limited to, plasma exposure ( $AUC_{0-t}$  and  $AUC_{tau}$ ),  $C_{max}$ ,  $T_{max}$ ,  $C_{min}$ ,  $CL/F$ ,  $AR$ , and  $MP$  ratio.  $N$ , mean, standard deviation, minimum, median, maximum, geometric mean, and coefficient of variation will be presented. The actual times of plasma sample collection will be used in the determination of the PK parameters. Details of PK analysis, including data handling rules and software used to perform PK analysis, will be provided in the PK SAP.

Individual and mean HMPL-523 and metabolite concentrations will be plotted by dose level.

HMPL-523

---

**APPENDIX 1. SCHEDULE OF ACTIVITIES**

Procedures	Study Day	Screening		Treatment 						Follow-up 		
		D-21 to D-1	D-7 to D-1	Cycle 1				Cycle 2		Cycle 3 and Onwards	Study Completion or Early Termination (30±7 Days After the End of Treatment)	Follow-up on Day 1 (±7) Quarterly After the End of Treatment
				D1	D8 (±1)	D15 (±1)	D22 (±1)	D1 (±3)	D15 (±3)			
Informed consent 	X											
Demographics 	X											
Medical history 	X											
Height	X											
Physical examination 	X		X	X	X	X	X	X	X	X		
ECOG performance status	X		X		X		X	X	X	X		
Vital signs 	X		X	X	X	X	X	X	X	X		
Concomitant medication/procedure 	X		X	X	X	X	X	X	X	X		
Hematology 		X		X	X	X	X	X	X	X		
Urinalysis/dipstick 		X			X		X	X	X	X		
Chemistry panel 		X		X	X	X	X	X	X	X		
Beta 2-microglobulin 		X					X		X	X		
Fasting lipid profile 		X					X		X	X		

HUTCHMED Ltd.

CONFIDENTIAL

HMPL-523

Procedures	Study Day	Screening		Treatment 						Follow-up 		
		D-21 to D-1	D-7 to D-1	Cycle 1				Cycle 2		Cycle 3 and Onwards	Study Completion or Early Termination (30±7 Days After the End of Treatment)	Follow-up on Day 1 (±7) Quarterly After the End of Treatment
				D1	D8 (±1)	D15 (±1)	D22 (±1)	D1 (±3)	D15 (±3)			
Serum amylase and lipase 		X		X	X	X	X	X	X	X		
Coagulation assay (INR, aPTT, PT) 		X					X		X	X		
17p del/TP53 mutation 	X											
Leukocyte immunophenotyping 	X			X		X		X				
HIV, HBV, and HCV screening 	X											
Pregnancy tests 	X									X		
Bone marrow examination (biopsy and/or aspirate) 	X											
Tumor biopsy 	X											
Echocardiogram/MUGA	X									X		
12-Lead ECG 	X		X	X		X			As clinically needed	X		
Arbor staging, IPI score, and Rai and/or Binet staging	X											

## HMPL-523

Procedures	Study Day		Treatment 							Follow-up 		
			Cycle 1				Cycle 2		Cycle 3 and Onwards			
	D-21 to D-1	D-7 to D-1	D1	D8 (±1)	D15 (±1)	D22 (±1)	D1 (±3)	D15 (±3)	D1 (±3)	Study Completion or Early Termination (30±7 Days After the End of Treatment)	Follow-up on Day 1 (±7) Quarterly After the End of Treatment	
Quantitative serum immunoglobulin levels (for WM/LPL) 	X						X		X	X	X	
CT/PET-CT 	X								X	X	X	
Tumor assessment 	X								X	X	X	
PK plasma sampling 			Refer to protocol Appendix 2 and Appendix 3									
Plasma collection for exploratory biomarkers 			X		X		X					
AE 	X		X	X	X	X	X	X	X	X		
HMPL-523 treatment			X									
Psychological evaluation	X											

AE=adverse event; ALP=alkaline phosphatase; ALT=alanine aminotransferase; aPTT=activated partial thromboplastin time; CLL=chronic lymphocytic leukemia; CR=complete response; CrCl=creatinine clearance; CT=computer tomography; D=day; DLT=dose-limiting toxicity; ECG=electrocardiogram; ECOG=Eastern Cooperative Oncology Group; HBsAg=hepatitis B surface antigen; HBcAb=hepatitis B core antibody; HBV=hepatitis B virus; HCV=hepatitis C virus; HIV=human immunodeficiency virus; HL=Hodgkin's lymphoma; IHC=immunohistochemistry; INR=international normalized ratio; IPI=International Prognostic Index; LDH=lactate dehydrogenase; LPL=lymphoplasmacytic lymphoma; MUGA=multigated acquisition scan; NHL=non-Hodgkin's lymphoma; PCR=polymerase chain reaction; PD=progressive disease; PET=positron-emission tomography; PK=pharmacokinetics; PR=partial response; PT=prothrombin time; QTcF=corrected QT interval with Fridericia; WM=Waldenström's macroglobulinemia.

 Informed consent must be documented before any study-specific screening procedure is performed.

---

 HMPL-523
 

---

-  Unless otherwise indicated, the visit window during the treatment period will be  $\pm 3$  days ( $\pm 1$  day during the DLT assessment window). Except for the ECG, echocardiogram, bone marrow biopsy, and/or aspirate and tumor assessment, all the assessments should be performed before dosing if the study drug is to be taken on the visit day. Unscheduled assessments could be performed if there is clinical indication.
-  Patients who complete or prematurely discontinue the study need to return to the study site for a follow-up within  $30 \pm 7$  days after the last dose of HMPL-523. Patients who discontinue the study drug due to reasons other than disease progression will remain on study and be followed quarterly until the patient has the first progression, starts new anticancer therapy, or dies, or until 12 months from the initial dose with the study drug have passed.
-  Demographic data include date of birth, gender, and self-reported race and ethnicity.
-  Medical history includes clinically significant diseases or symptoms, surgeries, cancer history (including constitutional symptoms/B symptoms [unexplained weight loss  $\geq 10\%$  over previous 6 months, fever  $>38^\circ\text{C}/100.5^\circ\text{F}$  for 2 or more weeks without other evidence of infection, night sweats for more than 1 month without evidence of infection]), prior cancer diagnosis (including tumor type, initial diagnosis date, IHC, flow cytometry, and other pathological findings), prior cancer therapies and procedures), use of tobacco, use of alcohol, and use of drugs of abuse prior to the screening visit.
-  Physical examination refers to the examination of all body systems, including assessment of head, eyes, ears, nose, larynx, neck, heart, chest, abdomen, limbs, skin, lymph nodes, nervous system, general condition and weight. After Cycle 1 Day 1, a change of physical signs from baseline, and newly presented or patient-reported physical signs should be evaluated. Height will be assessed only at screening.
-  Vital signs will include measurements of body temperature (taken under the armpit or in the mouth), heart rate, respiratory rate, and systolic and diastolic blood pressure while the patient is in a seated position. The patient should be seated for 5 minutes before the measurement of blood pressure.
-  Concomitant medications include all medications (eg, prescription drugs, over-the-counter drugs, herbal or homeopathic remedies, and nutritional supplements) used by the patient within 7 days prior to the screening visit and 30 days after the end of treatment. Any concomitant procedure (excluding bone marrow examination) within 7 days prior to the screening visit and 30 days after the end of treatment or early termination should be recorded.
-  Hematology consists of complete blood count, including red blood cell count, hemoglobin, hematocrit, reticulocyte count, white blood cell count with differential (neutrophils, bands, lymphocytes, eosinophils, monocytes, basophils, and other cells), and platelet count.
-  Urinalysis or dipstick (pH, specific gravity, glucose, protein, ketones, blood). If protein  $\geq 2+$  during the period of study treatment, a 24-hour urine test should be conducted within 1 week.
-  The chemistry panel includes blood urea nitrogen or urea, sodium, potassium, magnesium, chloride, calcium, phosphorus, fasting glucose, creatinine and estimated CrCl per Cockcroft-Gault, ALT, bilirubin direct and total, AST, ALP, LDH, uric acid, protein (total), and albumin.
-  Fasting lipid profile includes total cholesterol, high-density lipoprotein, low-density lipoprotein, and triglycerides.
-  17p del/TP53 mutation status is for patients with CLL only and optional.
-  Leukocyte immunophenotyping: T lymphocyte/B lymphocyte/natural killer cell counts (CD3, CD19, CD4, CD8, CD16/56) using a standard cell marker panel, should be tested at baseline and Weeks 3 and 5, every 4 weeks from Weeks 8-24, and then every 12 weeks thereafter until the end of treatment.
-  HBV: HBsAg and HBcAb; also HBsAb and HBV DNA by PCR if the patient is HBcAb positive; HCV: also HCV RNA by PCR if the patient is HCV antibody positive.
-  All women who are not postmenopausal ( $\geq 12$  months of nontherapy-induced amenorrhea) or surgically sterile will have a serum  $\beta$ -HCG test at screening. In the case of menopausal women, the date of menopause onset should be recorded.

---

**HMPL-523**

-  A bone marrow biopsy and/or aspirate is strongly recommended to be done at baseline or up to 3 months before Cycle 1 Day 1 and for confirmatory purposes when the patient is considered to be likely CR with CT assessment and laboratory tests results or to confirm suspected PD based solely upon declines in the platelet count and/or hemoglobin. If a bone marrow examination (biopsy and/or aspirate) has been performed within 3 months of Cycle 1 Day 1, a screening bone marrow examination does not need to be performed unless an investigator feels one is clinically warranted as outlined above. For those patients with initial bone marrow involvement from lymphoma/leukemia at study entry, a repeat biopsy at the end of therapy is necessary to confirm complete clinical response if physical examination and CT scans demonstrate a clinical CR or to confirm suspected PD based solely upon declines in the platelet count and/or hemoglobin. The number of additional/unscheduled bone marrow examinations performed during the study will be at the discretion of the investigator.
-  A 12-lead ECG should be performed at screening and/or pre-dose and at 4 hours  $\pm$  15 minutes post-dose on Days 1 and 15 in Cycle 1 and at any time on Day 1 of each cycle from Cycle 2 onwards. Triplicate ECGs, approximately 2 minutes apart, will be performed for all patients in baseline and Cycle 1. Additional ECGs and other cardiac monitoring will be provided as clinically indicated during the study. PR interval, QRS interval, RR interval, QT/QTcF interval, and heart rate will be involved in the 12-lead ECG.
-  Quantitative immunoglobulin assessment of IgM, IgA, IgG for all patients with WM/LPL. Quantitative immunoglobulin assessment should be repeated at the time of the CR confirmation.
-  Contrast-enhanced CT scans (neck, chest, abdomen, pelvis) should be performed for indolent NHL and/or PET-CT for HL and aggressive NHL.
-  The baseline tumor assessment can be completed within 21 days prior to enrolment. All measurable and evaluable lesions should be assessed and documented at this visit, using blood, physical examination and CT scan (neck, chest, abdomen, pelvis, liver/spleen) every 8 weeks (+/-7 days) for the first 24 weeks and then every 12 (+/-7 days) weeks thereafter. At study termination or early termination (other than disease progression) of the patients, tumor assessment will be also conducted. The same imaging procedure and laboratory tests used to define measurable lesions at baseline should be used throughout the study for each patient.
-  Blood samples should be collected according to the time-points tables in [Appendix 2](#) and [Appendix 3](#) of protocol Amendment 5. At the sponsor's discretion, some patients in the expansion stage may be required to provide samples for pharmacodynamics analysis. This will be based on certain signals as determined by the study team. The time points for these pharmacodynamic samples will be determined at the time of patient selection.
-  After informed consent, but prior to initiation of study medications, only SAEs caused by a protocol-mandated intervention will be collected (eg, SAEs related to invasive procedures such as biopsies, medication washout, or no treatment run-in). After initiation of HMPL-523 treatment, all AEs and SAEs regardless of attribution will be collected until 30 days following the last administration of study treatment or study discontinuation/termination, whichever is later. After this period, investigators should report only SAEs that are related to prior HMPL-523 treatment.
-  Preferably within 7 days prior to the first dose of the study drug.
-  Fresh or archival tumor tissue consisting of a cell block or 10 unstained slides should be collected for patients in dose expansion cohorts during screening.

HMPL-523

## APPENDIX 2. CTCAE CRITERIA TABLE FOR LAB PARAMETERS

PARAM (SI Unit)	Hypo	Hyper	ATOXGR			
			GRADE 1	GRADE 2	GRADE 3	GRADE 4
Hemoglobin (g/L)	Anemia	Hemoglobin increased	Increase in >0 - 2 g/dL	Increase in >2 - 4 g/dL	Increase in >4 g/dL	~
			Hemoglobin (Hgb) <LLN - 10.0 g/dL; <LLN - 6.2 mmol/L; <LLN - 100 g/L	Hgb <10.0 - 8.0 g/dL; <6.2 - 4.9 mmol/L; <100 - 80g/L	Hgb <8.0 g/dL; <4.9 mmol/L; <80 g/L	~
Platelets (10  /L)	Platelet count decreased		<LLN - 75,000/mm  ; <LLN - 75.0 x 10e9 /L	<75,000 - 50,000/mm  ; <75.0 - 50.0 x 10e9 /L	<50,000 - 25,000/mm  ; <50.0 - 25.0 x 10e9 /L	<25,000/mm  ; <25.0 x 10e9 /L
Neutrophils (10  /L)	Neutrophil count decreased		<LLN - 1500/mm  ; <LLN - 1.5 x 10e9 /L	<1500 - 1000/mm  ; <1.5 - 1.0 x 10e9 /L	<1000 - 500/mm  ; <1.0 - 0.5 x 10e9 /L	<500/mm  ; <0.5 x 10e9 /L
Lymphocytes (10  /L)	Lymphocyte count decreased	Lymphocyte count increased	<LLN - 800/mm  ; <LLN - 0.8 x 10e9/L	<800 - 500/mm  ; <0.8 - 0.5 x 10e9 /L	<500 - 200/mm  ; <0.5 - 0.2 x 10e9 /L	<200/mm  ; <0.2 x 10e9 /L
			~	>4000/mm  - 20,000/mm 	>20,000/mm 	~
Eosinophils (10  /L)		Eosinophilia	>ULN and >Baseline	~	Steroids initiated	~
Activated Partial Thromboplastin Time (sec)/Activated Partial Thromboplastin Time (RATIO)		Activated partial thromboplastin time prolonged	>ULN - 1.5 x ULN	>1.5 - 2.5 x ULN	>2.5 x ULN; bleeding	~
Prothrombin Intl. Normalized Ratio		INR increased	>1.2 - 1.5	>1.5 - 2.5	>2.5	~
Albumin (g/L)	Hypoalbuminemia		<LLN - 3 g/dL; <LLN - 30 g/L	<3 - 2 g/dL; <30 - 20 g/L	<2 g/dL; <20 g/L	~

HUTCHMED Ltd.

CONFIDENTIAL

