4.8.2 Secondary Safety Outcome Measures

- Incidence of TEAEs by NCI CTCAE v5.0 grade and associated dose of HMPL-523
- Incidence of Grade 3 and 4 abnormalities in safety-related laboratory parameters and associated dose of HMPL-523
- Incidence of TEAEs leading to HMPL-523 dose interruption, reduction, or treatment discontinuation

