### 17.4. LABORATORY EVALUATIONS

The following laboratory evaluations will be summarized in tables:

- Chemistry
- Coagulation
- Fasting lipid profile
- Hematology
- Leukocyte immunophenotyping
- Serum immunoglobulin
- Serum amylase and lipase
- Serum  $\beta$ -2 microglobulin
- Urinalysis

The following laboratory evaluations will be listed in listings:

- Chemistry
- Coagulation
- Fasting lipid profile

HMPL-523

- 
- Hematology
  - Leukocyte immunophenotyping
  - Serum immunoglobulin
  - Serum amylase and lipase
  - Serum  $\beta$ -2 microglobulin
  - Urinalysis
  - Pregnancy test
  - Viral serology

Quantitative laboratory measurements reported as “< X”, i.e. below the lower limit of quantification (LLQ), or “> X”, i.e. above the upper limit of quantification (ULQ), will be converted to X for the purpose of quantitative summaries, but will be presented as recorded, i.e. as “< X” or “> X” in the listings.

Descriptive statistics for all quantitative laboratory evaluations and change from the baseline will be presented in SI units for each visit.

For laboratory parameters graded by NCI CTCAE, version 5.0 (see [Appendix 2](#)), changes in CTC grade laboratory data will be summarized as shift table from baseline to worst post-baseline grade. Baseline CTCAE grade is derived from the last laboratory assessment prior to the first administration of study medication, as defined in [section 7.2](#). Worst (maximum) post-baseline CTCAE grade is derived with all measurements from the first dose administration of study medication to no more than 37 days after the last dose of study medication or new anti-cancer therapies, which comes earlier. Otherwise, the shift table will be presented by ‘normal’, ‘abnormal but not clinically significant’, ‘abnormal and clinically significant’.

All CTCAE Grade 1 or higher abnormalities in laboratory tests will be flagged in the listings.

The incidence of patients with the following abnormal liver function tests (Hy’s Law) at any time post baseline will also be summarized:

HMPL-523

- ALT or AST  $\geq 3$  x ULN and  $\leq 5$  x ULN
- ALT or AST  $\geq 5$  x ULN
- Total bilirubin  $\geq 2$  x ULN
- (ALT or AST  $\geq 3$  x ULN) and total bilirubin  $\geq 2$  x ULN
- (AST or ALT  $\geq 3$  x ULN) and total bilirubin  $\geq 2$  x ULN and ALP  $< 2$  x ULN

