## HMPL-523

			ATOXGR			
PARAM (SI Unit)	Hypo	Hyper	GRADE 1	GRADE 2	GRADE 3	GRADE 4
Glucose (mmol/L)	Hypoglycemia		<LLN - 55 mg/dL; <LLN - 3.0 mmol/L	<55 - 40 mg/dL; <3.0 - 2.2 mmol/L	<40 - 30 mg/dL; <2.2 - 1.7 mmol/L	<30 mg/dL; <1.7 mmol/L
Creatinine (umol/L)		Creatinine increased	>ULN - 1.5 x ULN	>1.5 - 3.0 x baseline if baseline was abnormal; >1.5 - 3.0 x ULN if baseline was normal	>3.0 x baseline-6.0xULN if baseline was abnormal; >3.0 - 6.0 x ULN if baseline is normal	>6.0 x ULN
Creatine Kinase (IU/L)		CPK increased	>ULN - 2.5 x ULN	>2.5 x ULN- 5 x ULN	>5.0 X ULN - 10.0 x ULN	>10.0 x ULN
Alkaline Phosphatase (IU/L)		Alkaline phosphatase increased	>ULN - 2.5 x ULN if baseline was normal; [a] 2.0 - 2.5 x baseline if baseline was abnormal [b]	>2.5 - 5.0 x ULN if baseline was normal; [a] >2.5 - 5.0 x baseline if baseline was abnormal [b]	>5.0 - 20.0 x ULN if baseline was normal; [a] >5.0 - 20.0 x baseline if baseline was abnormal [b]	>20.0 x ULN if baseline was normal; [a] >20.0 x baseline if baseline was abnormal [b]
Aspartate Aminotransferase (IU/L)		Aspartate aminotransferase increased	>ULN - 3.0 x ULN if baseline was normal; [a] 1.5 - 3.0 x baseline if baseline was abnormal [b]	>3.0 - 5.0 x ULN if baseline was normal; [a] >3.0 - 5.0 x baseline if baseline was abnormal [b]	>5.0 - 20.0 x ULN if baseline was normal; [a] >5.0 - 20.0 x baseline if baseline was abnormal [b]	>20.0 x ULN if baseline was normal; [a] >20.0 x baseline if baseline was abnormal [b]
Alanine Aminotransferase (IU/L)		Alanine aminotransferase increased	>ULN - 3.0 x ULN if baseline was normal; [a] 1.5 - 3.0 x baseline if baseline was abnormal [b]	>3.0 - 5.0 x ULN if baseline was normal; [a] >3.0 - 5.0 x baseline if baseline was abnormal [b]	>5.0 - 20.0 x ULN if baseline was normal; [a] >5.0 - 20.0 x baseline if baseline was abnormal [b]	>20.0 x ULN if baseline was normal; [a] >20.0 x baseline if baseline was abnormal [b]

HUTCHMED Ltd.

CONFIDENTIAL

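### SAP Appendix 2 misgrades two laboratory tests as written: 'Hemoglobin increased' has no reference point, and creatinine has an ungraded gap when baseline is above normal

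*SAP*

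**What the plan says.** SAP Section 17.4 grades laboratory results by NCI CTCAE version 5.0 and refers to Appendix 2 for the criteria. The grades feed a shift table from baseline grade to highest on-treatment grade. In addition, "All CTCAE Grade 1 or higher abnormalities in laboratory tests will be flagged in the listings". Protocol Section 4.8.2 lists as a secondary safety outcome: "Incidence of Grade 3 and 4 abnormalities in safety-related laboratory parameters and associated dose of HMPL-523".

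**Hemoglobin increased.** Grades 1, 2 and 3 read "Increase in >0 - 2 g/dL", "Increase in >2 - 4 g/dL" and "Increase in >4 g/dL". No cell says what the increase is measured from. Other rows do state their anchor; Grade 1 eosinophilia, for example, is ">ULN and >Baseline".

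**Creatinine.** Grade 1 runs from ULN to 1.5 x ULN, whatever the baseline. Grade 2 is ">1.5 - 3.0 x baseline if baseline was abnormal; >1.5 - 3.0 x ULN if baseline was normal". Grade 3 for an abnormal baseline runs from 3.0 x baseline to 6.0 x ULN, and Grade 4 is anything above 6.0 x ULN.

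Footnotes [a] and [b], which explain how normal and abnormal baselines are handled, are marked on ALP, AST, ALT, bilirubin and GGT. Neither hemoglobin nor creatinine carries them.

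**The concern.** A grading table should give every abnormal value exactly one grade, should never lower the grade as the value worsens, and should leave improvement ungraded. These two rows fail in opposite directions. The hemoglobin row can turn recovery into toxicity. The creatinine row can remove a grade from a patient who has worsened.

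Both kinds of patient can be enrolled. Protocol Section 5.1.2 excludes hemoglobin below 80 g/L but allows Stage 2 exceptions with sponsor approval, and Appendix 15 Table 12 foresees transfusion. The same section admits creatinine clearance down to 40 mL/min (Stage 1) or 30 mL/min (Stage 2), and lower with sponsor approval when the underlying disease is thought to be the cause.

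At stake is whether the shift tables and flagged listings can be trusted for these two tests and, for hemoglobin, whether spurious Grade 3 results enter a secondary safety outcome.

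**Working it through.** The plan states no figure on this point, so there is nothing to reproduce. The check applies the Appendix 2 bands literally.

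**Hemoglobin.** Increase = (post-baseline − baseline)/10, converting g/L to g/dL. The anemia grades use the same Appendix 2 row. The documents give no reference ranges, so LLN/ULN of 120/160 and 135/175 g/L are assumed.

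| Baseline to post (g/L) | Rise (g/dL) | 'Increased' grade, literal | Anemia grade, baseline to post |
|---|---|---|---|
| 85 to 86 | 0.1 | 1 | 2 to 2 |
| 85 to 105 | 2.0 | 1 | 2 to 1 |
| 85 to 115 | 3.0 | 2 | 2 to 1 |
| 85 to 126 | 4.1 | 3 | 2 to 0 or 1 |
| 80 to 121 | 4.1 | 3 | 2 to 0 or 1 |

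The last column depends on the assumed LLN. With a ULN anchor, none of these values has an 'increased' grade under either assumed range. On the literal reading the increase is zero at baseline, so no patient can have a baseline grade and every graded patient appears in the shift table as a worsening.

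As a rough guide to frequency, suppose hemoglobin does not truly change and all values are exchangeable without ties. The chance that at least one of m post-baseline values exceeds baseline is then m/(m+1). Protocol Section 5.6.9 schedules five draws in Cycles 1 and 2 (Days 8, 15 and 22; Days 1 and 15), giving 5/6 = 83%. This concerns Grade 1 or higher only.

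**Creatinine.** Work in ULN units with baseline b > 1. The bands are Grade 1 (1, 1.5], Grade 2 (1.5b, 3b], Grade 3 (3b, 6] and Grade 4 above 6. The ungraded interval is (1.5, 1.5b], with width 1.5(b − 1), up to the point where Grade 4 begins.

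| b | Grade at baseline | Ungraded interval | Grade 3 band | Overlap |
|---|---|---|---|---|
| 1.0 | none (normal) | none | (3, 6] | none |
| 1.2 | 1 | (1.5, 1.8] | (3.6, 6] | none |
| 1.4 | 1 | (1.5, 2.1] | (4.2, 6] | none |
| 1.6 | none | (1.5, 2.4] | (4.8, 6] | none |
| 2.0 | none | (1.5, 3.0] | empty | none |
| 2.5 | none | (1.5, 3.75] | empty | (6, 7.5] is Grade 2 and 4 |

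At b = 1.4, a value of 1.45 is Grade 1, 2.0 is ungraded and 2.2 is Grade 2, so grading is not monotone. A patient with a normal baseline who reaches 2.0 is Grade 2.

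A patient example: a 70-year-old, 70 kg man with creatinine 1.7 mg/dL has Cockcroft-Gault clearance (140 − 70) x 70/(72 x 1.7) = 40 mL/min and is not excluded by that criterion. A rise to 2.5 mg/dL is +47%. Grade 2 would need more than 1.5 x 1.7 = 2.55 mg/dL, and Grade 1 ends at 1.5 x ULN. The value is therefore ungraded for any ULN below 2.5/1.5 = 1.67 mg/dL. With an assumed ULN of 1.2 mg/dL, b = 1.42 and the new value is 2.08 x ULN.

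**The case against.** **Hemoglobin.** The cell does not say 'from baseline'. The column marks a high-side abnormality and the plan names CTCAE v5.0, so a programmer might infer 'above normal'. That is fair: what is established is a missing reference point, and 'any rise' is the literal reading. Still, nothing in the SAP supplies the inference, and neighbouring rows state their anchors. Anemia is a separate direction in the same row, so recovery can also be shown there, but the rise would still be graded and flagged.

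**Creatinine.** A reader might infer that renal worsening goes unreported or that kidney-injury events of special interest are missed. The documents do not support this. SAP Section 17.2.9 and Table 3 identify those events by a MedDRA search of adverse event terms, not by Appendix 2. SAP Section 17.4 summarises creatinine and its change by visit and lists the chemistry results. Investigator-graded adverse events are separate.

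A reader might also infer that the creatinine gap changes the Grade 3/4 outcome. It does not: the ungraded interval lies below 3b, where Grade 3 would start, and every value above 6 x ULN is Grade 4. The overlap for b > 2 is naturally settled by SAP Section 7.3, which takes the highest grade as the worst value. That same rule means one on-treatment value between 1 and 1.5 x ULN keeps a patient at Grade 1 in the shift table, although each value in the gap still loses its listing flag.

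**Size.** The 83% is not a forecast. Rounding produces ties, which lower it, and it says nothing about Grade 3, which needs a rise above 4 g/dL. Nor does the table conflict generally with the response criteria: rising hemoglobin counts toward response only under the CLL criteria (SAP Appendix 4), and the two CLL cohorts are 1 + 7 = 8 of 48 expansion patients.

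**Conclusion.** Both rows are wrong as written and should be corrected.

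- **Hemoglobin:** on the literal reading, recovery or transfusion is flagged as Grade 1 or 2, and as Grade 3 when the rise exceeds 4 g/dL. This enters the listings and shift tables, and potentially the Grade 3/4 laboratory outcome, for which SAP Section 17.4 names no other source of grades. How often Grade 3 would occur cannot be derived from the documents.
- **Creatinine:** for any baseline above ULN, values in (1.5, 1.5b] x ULN have no grade. A baseline above 1.5 x ULN is itself ungraded, the Grade 3 band is empty for b of 2 or more, and Grades 2 and 4 overlap for b above 2. The damage is confined to the derived grade, the flag and the shift count.

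The creatinine result is arithmetic on the table, taking 'abnormal' to mean above ULN. The statement that Grade 3/4 incidence is unaffected assumes that the higher grade is used in the overlap. The hemoglobin result rests on the literal reading. No comparison with the CTCAE text was made, because it is not in the documents.

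**What to change.** In SAP Appendix 2:

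1. **Hemoglobin increased:** grade only values above ULN, by the size of the increase above ULN, or above baseline if baseline exceeds ULN.
2. **Creatinine, abnormal baseline:** make the bands contiguous so that every value above ULN has a grade, for example by extending Grade 1 from above ULN to the lower limit of Grade 2.
3. **Rule for the creatinine row:** assign the highest grade whose limit is met, so that anything above 6 x ULN is always Grade 4.

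Item 2 is a choice to be made explicitly. Extending Grade 1 puts the move from 1.4 to 2.0 x ULN at Grade 1, so the shift table shows no change. Starting Grade 2 above 1.5 x ULN would put it at Grade 2. Either closes the gap.

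The cost is two table rows and the grading program. SAP Section 2 allows revisions before the final database lock.
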